**Patient – Follow-up:**

- At 1, 3, and 6 months post-baseline, patients will complete follow-up questionnaires via an online questionnaire, which will assess: 1) presence of TMJ noise, 2) presence of jaw or temple pain including frequency, duration, intensity, 3) pain-related disability; 4) factors that increase or decrease their pain, and 4) whether the jaw pain is getting better, worse or staying the same.

**OMS and DAs – During data collection phase:**

- Both the OMS and any DA(s) who assisted in the procedure(s) and was responsible for using the device during the procedure, and consented to study participation, will each complete a questionnaire about their experience with the jaw support device once during recruitment and once at the end of recruitment. This questionnaire assesses; 1) use of the device compared to a dental assistant holding the jaw, 2) ease and stability of device use, 3) provider's comfort and posture when using the device, 4) fit and manipulation of device before and during procedure, 5) ease of removal of device, 6) efficiency of procedure with device, 7) interference with working field when device is used, 8) airway support with device, 9) impact of dental assistant's other duties with use of the device, 10) use of device in future, 11) thoughts on minimizing injury during procedures, 12) overall opinion of device and 13) any suggestions for modification of the device.

## 9 ASSESSMENT OF SAFETY

### 9.1 Specification of Safety Parameters

Safety monitoring for this study will focus on unanticipated problems (UPs) involving risks to participants, including UPs that meet the definition of a serious adverse event (SAE).

#### 9.1.1 *Unanticipated Problems*

The Office for Human Research Protections (OHRP) considers UPs involving risks to subjects or others to include, in general, any incident, experience, or outcome that meets **all** of the following criteria:

- unexpected in terms of nature, severity, or frequency given (a) the research procedures that are described in the protocol-related documents, such as the IRB-approved research protocol and informed consent document; and (b) the characteristics of the subject population being studied;
- related or possibly related to participation in the research (“possibly related” means there is a reasonable possibility that the incident, experience, or outcome may have been caused by the procedures involved in the research); and
- suggests that the research places subjects or others at a greater risk of harm (including physical, psychological, economic, or social harm) than was previously known or recognized.

Per the definition, only a subset of adverse events would be characterized as UPs. There are other types of incidents, experiences, and outcomes that are not considered adverse events (AEs), but are characterized as UPs (e.g., breach of confidentiality or other incidents involving social or economic harm).

#### 9.1.2 *Adverse Events*

An AE is any untoward or unfavorable medical occurrence in a human subject, including any abnormal sign (for example, abnormal physical exam or laboratory finding), symptom, or disease, temporally associated with the subject’s participation in the research, whether or not considered related to the subject’s participation in the research.

#### 9.1.3 *Serious Adverse Events*

A SAE is one that meets one or more of the following criteria:

- Results in death

- Is life-threatening (places the subject at immediate risk of death from the event as it occurred)
- Results in inpatient hospitalization or prolongation of existing hospitalization
- Results in a persistent or significant disability or incapacity
- Results in a congenital anomaly or birth defect
- An important medical event that may not result in death, be life threatening, or require hospitalization may be considered an SAE when, based upon appropriate medical judgment, the event may jeopardize the subject and may require medical or surgical intervention to prevent one of the outcomes listed in this definition.

## **9.2 Time Period and Frequency for Event Assessment and Follow-Up**

UPs will be recorded in the data collection system throughout the study.

The PI will record all safety events with start dates occurring any time after informed consent is obtained until 7 (for non-serious AEs) or 30 days (for SAEs) after the last day of study participation. Events will be followed for outcome information until resolution or stabilization.

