Patient-reported data will be collected via tablets, smart-phones, or computers at baseline during in-office visit(s) with the surgeons. To assist with in-office data collection, participating OMS will be offered tablets. OMS, dental assistants, and patients will provide baseline and follow-up data directly into the electronic data capture (EDC) system that is maintained by the HealthPartners Data Coordinating Center (DCC); data can be entered via tablets, smart-phones, or computers. After baseline, patient-reported data will be ascertained independent of office visits, and all follow-up patient, OMS and dental assistant data collection will be managed by HP DCC. Follow-up contacts to non-responders will also be managed by the DCC.

- **Overview of Study Schedule**

- The electronic data system used to collect patient and OMS/dental assistant data will be assessed for acceptability and compatibility prior to administration of any questionnaires.
- OMS and their office staff will receive study training from the Study Coordinator (SC), after which the OMS is authorized to begin enrolling study patients.
- An in-office patient log will be kept regarding the reason patients were excluded or declined to participate.
- Once the patient is screened using the *Screening Questionnaire* that comprises the inclusion and exclusion criteria, patients who are eligible will be invited to participate in the study. Potential patients who are interested in study participation will undergo consent procedures.
- Patients will complete these baseline forms and questionnaire before surgery: *Patient Contact and Patient Demographics information*, and *Patient Baseline Questionnaire*.
- Randomization procedures will occur, and patients will receive their randomized assignment.
- The OMS will complete the *Doctor Surgery Questionnaire* after completing the 3rd molar extractions.
- At 1, 3, and 6 months post-baseline, patients will complete follow-up assessments via an online questionnaire. Non-responders will be followed up with email, telephone, and/or texting. All patients will be followed up regardless of whether they report TMD pain at any follow-up.

- Midway through and at the end of the enrollment phase of the study, the OMS and dental assistants will complete a questionnaire regarding their experience with the use of the device.

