### 7.4 Final Study Follow-up

#### Follow-up 3 at 6-Months (Day 180 ± 2 weeks)

- Patients will complete their *Patient Six-Month Follow-up Questionnaire* six-months post baseline independent of an in-office visit.

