### **7.7 Unscheduled Visit**

For the purpose of the study, the patient does not need to see the surgeon after their 3rd molars are surgically removed. However, the patient may return to the OMS with concerns after surgical removal of their 3rd molars, including that they are having TMD pain. If the OMS determines that the concern is related only to 3rd molar removal, as described in their inter-office consent form for 3rd molar removal, then they will manage the patient for this. This includes the presence of TMD pain. If the OMS cannot determine if the concern is related to the study or believes it is related to the study, including use of the device, then they will inform the study coordinator who will discuss this event with the project PI. If they deem the event to be an adverse event related to the study, then it will be reported as described in Section 9.4.

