### **16.3 Types of Data**

The OMS or their DA will complete the:

- Screening Questionnaire
- Doctor Surgery Questionnaire
- Doctor Questionnaire Regarding Use of Device
- Dental Assistant Questionnaire Regarding Use of Device

The patients will complete:

- Patient Contact Information
- Patient Demographics
- Patient Baseline Questionnaire
- Patient 1-, 3- and 6-Month Follow-up Questionnaires.

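### All AEs are to be recorded until 7 or 30 days after participation ends, but no scheduled contact after surgery is described as asking about them

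*Combined protocol and SAP*

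**What the plan says.** **What must be recorded.** Section 9.2 has the PI record every safety event that starts between consent and a cut-off: "until 7 (for non-serious AEs) or 30 days (for SAEs) after the last day of study participation". The definition in 9.1.2 is wide ("An AE is any untoward or unfavorable medical occurrence in a human subject") and applies whether or not the event is thought related to the research. Sections 12.3.1 and 16.1 put recording on the surgeons and their staff. Section 9.5 repeats that all AEs will be recorded and has the data coordinating center (DCC) track them.

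**What the counts are for.** Section 9.5 sets a Lan-DeMets stopping rule, applied separately to the any-AE and any-SAE outcomes, with the arms compared by Fisher's exact test.

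**How patients are followed.** Section 4 says: "After baseline, patient-reported data will be ascertained independent of office visits". Section 7.7 says: "For the purpose of the study, the patient does not need to see the surgeon after their" third molars are out; patients may return if they have a concern. The scheduled patient data after surgery are the "Patient 1-, 3- and 6-Month Follow-up Questionnaires" (16.3), the last at "Day 180 ± 2 weeks" (7.4). Section 8.1 describes their content: "which will assess: 1) presence of TMJ noise, 2) presence of jaw or temple pain including frequency, duration, intensity, 3) pain-related disability", then factors that change the pain and whether it is improving.

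**Where AEs would appear.** Appendix A has no AE row, and the lists in Sections 13 and 16.3 name no AE form. Patients, surgeons and dental assistants all know the assignment (5.4.2).

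**The concern.** The duty to record and the means of finding out do not match. The people told to record AEs have no scheduled contact with the patient after surgery. The contacts that are scheduled belong to the DCC and, as described, ask about the jaw only. A patient treated elsewhere three weeks later for something other than jaw pain could complete every questionnaire as described in 8.1 with no prompt to mention it.

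At stake are the inputs to the 9.5 rule and the safety material in the six-monthly Medical Monitor report (Sections 10 and 16.4). Incomplete counts weaken any signal. Because reporting is voluntary and the trial is open, completeness could also differ between arms.

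**Working it through.** The plan gives no figure for AE rates or AE capture, so there is none to reproduce. The check traces each kind of event from occurrence to record, then works out the windows.

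**1. Routes by which an event could be learned of**

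| Event | Described route | Solicited from every patient? |
|---|---|---|
| During surgery, including device slippage or pressure loss (2.3.1, 12.3.1) | Surgeon present; Doctor Surgery Questionnaire for both arms, including device discontinuation (8.1) | Observable in all, though the listed content has no general AE item |
| Jaw or temple pain and pain-related disability, months 1 to 6 | The three questionnaires (8.1) | Yes, but no rule sends answers to AE records |
| Any other event after the day of surgery | Patient returns to the surgeon (7.7), or volunteers it to the DCC or PI | No |
| Any event after the 6-month questionnaire | As the row above | No |

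For a returning patient, 7.7 describes passing the matter on only when the surgeon suspects a link to the study or cannot tell. It has no step for recording the rest, although 9.1.2, 12.3.1 and 16.1 together still require it.

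**2. Window against contact**

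Inputs: last contact at Day 180 ± 14 (7.4); cut-offs of 7 and 30 days (9.2). Assumption: the last day of participation is the day of the 6-month questionnaire.

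- AE window closes at last contact + 7: 180 + 7 = Day 187 (range 166 + 7 = 173 to 194 + 7 = 201).
- SAE window closes at last contact + 30: 180 + 30 = Day 210 (range 166 + 30 = 196 to 194 + 30 = 224).
- Scheduled post-surgery contacts described as asking about AEs: 0 of 3.
- Scheduled contacts between the 6-month questionnaire and either cut-off: 0.

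**3. How sensitive the 9.5 comparison is to capture**

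The rates here are assumptions, used only to show sensitivity. Recorded risk = true risk × share captured. The setting is 294 / 2 = 147 per arm and one two-sided Fisher test at 0.05, without the sequential boundary.

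| True risk, device v Usual Care | Captured, device v Usual Care | Recorded | P(significant) |
|---|---|---|---|
| 20% v 10% | 100% v 100% | 20% v 10% | 0.62 |
| 20% v 10% | 50% v 50% | 10% v 5% | 0.29 |
| 20% v 10% | 30% v 30% | 6% v 3% | 0.15 |
| 20% v 10% | 50% v 30% | 10% v 3% | 0.61 |
| 20% v 10% | 30% v 50% | 6% v 5% | 0.035 |
| 10% v 10% | 100% v 100% | 10% v 10% | 0.033 |
| 10% v 10% | 50% v 30%, or the reverse | 5% v 3%, or the reverse | 0.076 |

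Equal under-capture alone costs much of the power to see a harm. Unequal capture can hide a real difference or suggest a false one, depending on its direction, and the documents do not indicate the direction.

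**The case against.** **The device risks are intra-operative.** The device is used once, and the risks the protocol names occur in front of the surgeon and assistant. This stands. A reader might infer that AE counts come only from patients who choose to return; the documents do not support that, because the surgeon attends every operation and completes a form for every patient in both arms. The gap concerns later events.

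**The most relevant late harm is asked about.** Jaw pain, its intensity and related disability are solicited from everyone, with follow-up of non-responders. This also stands, except that no rule turns those answers into AE records.

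**The forms were not seen.** Section 8.1 summarises the questionnaires. The case report forms, surgeon manual and data management plan are separate documents (Supplemental Materials). The lists in Sections 13 and 16.3 are not conclusive either: 9.4.1 names a Serious Adverse Event Form and a report form for unanticipated problems, and neither is listed there. So the finding is that AE solicitation is not described, not that it is known to be absent.

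**Little rests on the counts.** A reader might infer that a final-report safety comparison would be invalid. Section 12.4 plans no AE comparison, 12.3.1 says there is no specific safety outcome, and 9.1 focuses monitoring on unanticipated problems. Section 12.3 plans no interim analysis, and the exact sequential plan needs funder approval before any formal test. Even so, 9.5 does commit to recording all AEs and to a between-group rule on them, and an unanticipated problem cannot be identified if the event is never learned of.

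**The 7/30-day window promises no contact.** Fair: it says which start dates qualify, and a spontaneous report can fall within it. A reader might say the window cannot be met; what the text supports is that nothing in it is actively sought.

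**Oversight was matched to risk.** The device was judged non-significant risk, and oversight was set after Medical Monitor review. Passive collection is a defensible choice, but the protocol should then say so.

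**Conclusion.** The point holds for events after the day of surgery other than jaw pain and disability. The protocol commits to recording all of them, to about Day 187 for AEs and Day 210 for SAEs, yet describes no scheduled contact that asks. Such events are likely to be under-counted. Capture could also differ by arm, because patients and surgeons know the assignment. A reader might infer that the bias favours the device, since its patients might return less often. The opposite is equally possible, and nothing in the documents decides between them.

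The size cannot be derived from the documents, which give neither an AE rate nor a reporting rate. The conclusion assumes that the 8.1 summary reflects the actual questionnaires and that participation ends with the 6-month questionnaire. The primary outcome and its analysis are not touched. This should be corrected because the remedy is cheap and uses existing contacts.

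**What to change.** 1. Add one item, worded identically in both arms, to the 1-, 3- and 6-month questionnaires: for example, any unplanned medical or dental care, or hospitalisation, since surgery or the last questionnaire.
2. Have the DCC route positive answers to the PI for AE/SAE recording under 9.2. State whether jaw-pain and disability answers are also AE records or are counted as outcomes only.
3. Add an AE row to Appendix A, and an AE form to Sections 13 and 16.3.
4. In 9.2, either end the collection window at the 6-month questionnaire or state that the extra 7 and 30 days rest on spontaneous reports.
5. If the case report forms already contain such an item, describe it in 8.1 and Appendix A instead of adding one.

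**Cost.** A protocol amendment, one question and a routing rule, with no added visits. At most 294 × 3 = 882 answers would need checking. Many positive answers will be minor or unrelated, and all count under 9.1.2, so the any-AE outcome in 9.5 will carry more background events. An item limited to care received keeps that load down, but leaves milder events to spontaneous report, which 9.2 should then say. Recall is also imperfect: the longest nominal interval is 180 − 90 = 90 days.

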## **9.3 Characteristics of an Adverse Event**

### ***9.3.1 Relationship to Study Intervention***

To assess relationship of an event to study intervention, the following guidelines are used:

1. Related (Possible, Probable, Definite)
  - a. The event is known to occur with the study intervention.
  - b. There is a temporal relationship between the intervention and event onset.
  - c. The event abates when the intervention is discontinued.
  - d. The event reappears upon a re-challenge with the intervention.
2. Not Related (Unlikely, Not Related)
  - a. There is no temporal relationship between the intervention and event onset.
  - b. An alternate etiology has been established.

### **9.3.2 *Expectedness of AEs***

The PI will be responsible for determining whether an AE is expected or unexpected. An AE will be considered unexpected if the nature, severity, or frequency of the event is not consistent with the risk information previously described for the intervention.

### **9.3.3 *Severity of Event***

The following scale will be used to grade AEs:

1. Mild: no intervention required; no impact on activities of daily living (ADL)
2. Moderate: minimal, local, or non-invasive intervention indicated; moderate impact on ADL
3. Severe: significant symptoms requiring invasive intervention; subject seeks medical attention, needs major assistance with ADL

## **9.4 *Reporting Procedures***

### **9.4.1 *Unanticipated Problem Reporting to IRB and NIDCR***

Incidents or events that meet the OHRP criteria for UPs require the creation and completion of a UP report form. OHRP recommends that investigators include the following information when reporting an adverse event, or any other incident, experience, or outcome as a UP to the IRB:

- appropriate identifying information for the research protocol, such as the title, investigator's name, and the IRB project number;
- a detailed description of the AE, incident, experience, or outcome;
- an explanation of the basis for determining that the AE, incident, experience, or outcome represents a UP;
- a description of any changes to the protocol or other corrective actions that have been taken or are proposed in response to the UP.

To satisfy the requirement for prompt reporting, UPs will be reported using the following timeline:

- UPs that are serious adverse events will be reported to the IRB and to NIDCR within 1 week of the investigator becoming aware of the event.

- Any other UP will be reported to the IRB and to NIDCR within 2 weeks of the investigator becoming aware of the problem.
- All UPs should be reported to appropriate institutional officials (as required by an institution's written reporting procedures), and OHRP within one month of the IRB's receipt of the report of the problem from the investigator.

All UPs, including UPs that are SAEs, will be reported to NIDCR through the Rho Product Safety centralized reporting system:

- Product Safety Fax Line (US): [name]
- Product Safety Fax Line (International): [contact]
- Product Safety Email: [rho\\[contact]](mailto:[contact])

General questions about SAE reporting can be directed to the Rho Product Safety Help Line (available 8:00AM – 5:00PM Eastern Time):

- US: [name]
- International: [contact]

For any UP meeting the SAE criteria, the study surgeon will complete a Serious Adverse Event Form and will submit via fax or email within the timelines stated in Section 9.4.1 to NIDCR's centralized safety system via Rho Product Safety. Once submitted, Rho Product Safety will send a confirmation email to the investigator within 1 business day. The investigator should contact Rho Product Safety if this confirmation is not received. This process applies to both initial and follow-up SAE reports.

#### **9.4.2 Reporting of SAEs and AEs to FDA**

The FDA determined that the RJ2 device is a non-significant risk (NSR) device, and thus the FDA determined that an IDE application is not required to be submitted or approved by the FDA. The FDA further stated that IRB approval of the investigation as a NSR study must be obtained. Therefore, reporting of SAEs and AEs will be to the University of Minnesota and HealthPartners IRBs. NIDCR will be copied on any reports.

#### **9.5 Halting Rules**

For monitoring purposes, all AEs will be recorded throughout the trial, and the DCC will track all AEs, including all SAEs.

Decisions about stopping the trial will be made either by the investigators or by the NIDCR in consultation with the Medical Monitor. A formal stopping rule will use the group sequential method of Lan and DeMets, described in more detail in Section 12.3.2, applied separately to the two outcomes "Any AE" and "Any SAE", with P-values computed comparing the groups according to these outcomes using Fisher's exact test. As noted in 12.3.2 regarding efficacy, the exact sequential monitoring plan must be reviewed and approved by the NIDCR in consultation with the MMOR before any interim formal tests occur.

The investigators can stop enrollment in the study at any time based on the occurrence of an AE or UP that they deem of sufficient concern.

---

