Over 10 million 3rd molars (wisdom teeth) are extracted from about 5 million people in America each year.(1) More than 11 million patient days of “standard discomfort or disability” – pain, swelling, bruising and malaise – result postoperatively.(1) Although the American Association of Oral and Maxillofacial Surgeons guidelines state that consent forms for 3rd molar extractions should include injury to the temporomandibular joint (TMJ) or associated muscles(17), there are few reports of the trauma to the TMJ or jaw muscles from this procedure.(1) One of the best studies assessing development of TMD after 3rd molar extractions is a large prospective cohort study of young adults.(3) Huang et al. assessed the onset of jaw joint symptoms (i.e., TMJ noise and jaw pain) in individuals who had 3rd molar extractions compared to those who did not. Of the 517 participants with follow-up data, 39% (n = 201) had a total of 720 3rd molars extracted, with 68% reporting that 'intravenous sedation' or general anesthesia was used. Among patients undergoing 3rd molar removal, the rate of TMD lasting more than 1 month was 34.3 per 100 person-years compared to 8.8 among those who did not have 3rd molar extractions. The relative risk of developing TMD was 3.8 and the rate of TMD reported by patients undergoing this surgery was greater than 30%. This study's findings are limited by its low follow-up rate (40 to 50% for follow-up questionnaires at different intervals). Further, a retrospective study reported that almost a quarter of new onset TMD cases in young adults were associated with 3rd molar removal.(2) In a cross-sectional study of patients aged 18.7 + 1.1 years, the occurrence of 3rd molar extractions was significantly associated with TMD ( $P<0.001$ ). (7) Finally, in an age and sex matched case-control study, at 6 months follow-up, patients who had 3rd molar extractions had significantly more TMJ and jaw muscle pain than controls who did not have this surgery ( $P<0.05$ ). (6) These findings suggest removing 3rd molars is associated with development of TMD and that this patient safety issue is not addressed by current methods to protect the jaw during this surgery. Providing better support for

the jaw during 3rd molar extractions to prevent hyperextension and excessive force on the jaw would be expected to alleviate the physical stress on the jaw and reduce patient suffering and jaw injury. (18, 19)

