## 12.3 Planned Interim Analyses (if applicable)

No interim analyses are planned.

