### 12.3.1 Safety Review

If the device becomes loose or excessive force is placed on it during the procedure, there is a potential risk this could compromise the support of the patient's jaw, resulting in jaw injury.

While the proposed intervention does not include changes to practice that may harm patient participants, a special focus will be the safety of patients exposed to the study intervention.

We have no specific outcome measures related to safety but participating surgeons will be required to record all AEs, including SAEs, according to procedures specified in Section 9.2

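### The formal stopping rule monitors 'Any AE' and 'Any SAE' but gives the named device risk, jaw injury from lost support, no outcome of its own; 'Any AE' as defined dilutes a non-serious excess

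*Combined protocol and SAP*

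**What the plan says.** - **Halting rule (9.5).** "A formal stopping rule will use the group sequential method of Lan and DeMets". It is applied separately to 'Any AE' and 'Any SAE', "with P-values computed comparing the groups according to these outcomes using Fisher's exact test". The section also says that every AE is recorded, and that investigators may stop enrollment at any time over an AE or unanticipated problem that concerns them.
- **AE definition (9.1.2).** "An AE is any untoward or unfavorable medical occurrence in a human subject, including any abnormal sign". Symptoms count too, "whether or not considered related to the subject’s participation in the research". No section removes expected surgical sequelae from the definition or from 'Any AE'.
- **Background (2.1).** The usual aftermath of this surgery is listed as "pain, swelling, bruising and malaise". The section gives national totals and no per-patient rate.
- **Named risk (2.3.1, 12.3.1).** The device may slip, loosen or lose pressure, compromising jaw support; 12.3.1 says jaw injury could follow. The same section says: "We have no specific outcome measures related to safety".
- **Unscheduled visits (7.7).** No post-operative study visit is needed. The surgeon manages concerns judged due only to the extraction, TMD pain included. Events deemed study-related are reported under 9.4.
- **Interim analyses (12.3).** "No interim analyses are planned". Section 12.3.2 names an O'Brien-Fleming spending function with total alpha 0.05, should looks be held.

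**The concern.** A composite of all adverse events can show a device harm only to the extent that patients would not have had an AE anyway. An EC patient who has routine swelling already counts as an event, and a jaw injury on top adds nothing to the comparison. The more common routine AEs are, the less of any excess reaches the test.

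Jaw injury from lost support is the harm the protocol singles out. An injury that meets the SAE criteria enters 'Any SAE'. One that does not can enter the formal rule only through 'Any AE'. What is at stake is whether a non-significant 'Any AE' comparison says anything useful about that harm.

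**Working it through.** **The plan's own figures.** The safety rule has no stated event rate, boundary or power, so there is nothing of its own to reproduce. The sample size does reproduce: 14% versus 28%, 80% power and two-sided 5% give 132 per group, and 264/0.90 rounds up to 294. With 1:1 allocation, 294/2 = 147 per arm.

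**Inputs.** From the plan: 147 per arm, Fisher's exact test, total alpha 0.05, O'Brien-Fleming-type spending. Assumed, because the documents give no values: a background risk *b* of any other AE, equal in both arms; the device adds jaw injury in 10% of EC patients, independently of other AEs; the test is two-sided; all events are recorded.

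**Formulas.** UC any-AE risk = *b*. EC any-AE risk = *b* + (1 − *b*) × 0.10. Power is the sum of the two binomial probabilities over all outcome pairs that Fisher's test rejects. Two settings are used:
- Final look: 147 per arm at the full 0.05. This flatters a sequential rule.
- One look at half information: 73 per arm, alpha = 2(1 − Φ(1.96/√0.5)) = 0.0056.

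**'Any AE'.**

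| Background *b* (UC) | EC risk | Power, final look | Power, half-information look |
|---|---|---|---|
| 5% | 14.5% | 75% | 14% |
| 10% | 19.0% | 54% | 7% |
| 25% | 32.5% | 25% | 2.5% |
| 50% | 55.0% | 12% | 1% |
| 80% | 82.0% | 5% | 0.4% |
| 95% | 95.5% | 3% | 0.1% |

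Counting only rejections in the direction of harm barely changes this: at 95% the final-look figure goes from 2.6% to 1.9%.

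**Ceiling.** Even if all 147 EC patients had an AE, the test reaches 0.05 only when 141 or fewer UC patients do (141/147 = 96%). At the half-information look the limit is 64 of 73 (88%).

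**A jaw/device-specific outcome, same 10% excess.**

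| UC | EC | Final look | Half-information look |
|---|---|---|---|
| 1% | 1% + 99% × 0.10 = 10.9% | 96% | 26% |
| 2% | 2% + 98% × 0.10 = 11.8% | 91% | 22% |
| 14% | 14% + 86% × 0.10 = 22.6% | a little over 42% | 5% |

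The last row shows what happens if the outcome is drawn so widely that it takes in TMD pain at the 14% used in 12.2.

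**Recording.** Sections 9.1.2 and 9.5 call for every AE, related or not. Section 7.7 describes clinical management for extraction-only concerns and reporting for study-related ones. It does not say that the rest go unrecorded, but it names no step that records them. The follow-up questionnaires (8.1) cover TMJ noise, jaw or temple pain and related disability, not AEs in general.

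**The case against.** The strongest counter-argument is that the background may be low in practice. Section 2.3.1 treats extraction risks as normal care, 7.7 requires no visit, and AEs are entered by surgeons and staff. At a 5–10% background, 'Any AE' keeps 54–75% power at the final look. This stands, and it rules out two inferences that a reader might draw.

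- **That nearly every patient will have a recorded AE.** The 2.1 totals give 11 million patient days over about 5 million people, roughly 2.2 days each. That is an average duration, not the share of patients affected, and it says nothing about recording in this trial.
- **That the rule cannot detect jaw injury at all.** An injury meeting the SAE criteria enters 'Any SAE', and no section grades the injury as non-serious. Unanticipated-problem reporting, Medical Monitor reports about every six months and discretionary stopping also remain. Jaw pain is itself the primary outcome, although interim outcome data are withheld from study staff and investigators.

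What does not stand is the idea that sparse recording rescues the rule. The route in 7.7 that would keep routine sequelae out names TMD pain, so it could keep the jaw injury out as well. The 54–75% holds only if those injuries are recorded.

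Two further points are fair. The gain from a specific outcome is large only at the final look, when there is nothing left to stop. And 9.5 requires approval of the exact sequential plan before any formal interim test, so it can be read as conditional and its conflict with 12.3 as one of wording. Even so, 9.5 already fixes the two outcomes and speaks of a formal rule that will be used.

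**Conclusion.** The point holds in a limited form. If AEs are recorded as 9.1.2 defines them, the formal rule has little power for a non-serious jaw-injury excess: for an assumed 10% excess, 25% at a 25% background, 12% at 50% and 3% at 95%, all at full alpha at the final look. If recording follows 7.7, the background falls but the injury may be lost too. Either way, the one device harm that the protocol names is not a monitored outcome.

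The size depends on the assumed 10% excess, its independence from other AEs and the unknown background. A specific outcome is clearly better at the final look (91–96% with 1–2% in UC), but gives only about 22–26% at a half-information look, so it improves the rule without making early stopping likely. The primary efficacy analysis is not affected.

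**What to change.** 1. In 9.5, add a pre-specified monitored outcome of jaw/TMJ injury or loss of jaw support, ascertained and recorded identically in UC and EC, alongside 'Any SAE'. Define it so that it does not simply reproduce the TMD-pain endpoint; the 14% row shows the cost of a wide definition.
2. Either exclude an arm-neutral list of expected extraction sequelae from 'Any AE', or keep 'Any AE' as a descriptive summary. Continue to record all AEs.
3. Reconcile 9.1.2 and 9.5 (all AEs recorded) with 7.7 (study-related events reported), stating what is recorded when a concern is put down to the extraction.
4. Reconcile 9.5 (formal sequential rule) with 12.3 (no interim analyses planned), stating whether safety tests will be done and, if so, when.

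**Cost.** Mainly protocol wording and one agreed list applied to AE records already kept. Recording lost support in both arms probably needs an item on the Doctor Surgery Questionnaire, since 8.1 asks about discontinuation only where the device was used. The list must be agreed in advance, and an unlisted non-serious effect would then appear only in the descriptive tables.
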